### **4.2 Inclusion criteria (must)**

Subjects must meet all of the following inclusion criteria to be enrolled in the study:

Voluntary signed the written ICF.

- 1) Age was over 18 and 75 at the time of enrollment, acceptable for both men and women.
- 2) The Eastern Cooperative Oncology (ECOG) physical performance score was 0 or 1.
- 3) Expected survival is greater than 3 months.
- 4) Histologically or cytologically confirmed nasopharyngeal carcinoma.
- 5) The subject had previously failed treatment with PD-1 inhibitor and had no indication for radical local treatment.

6) According to the efficacy evaluation criteria of solid tumors RECIST v 1. And 1 with at least one measurable lesion.

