#### **4.3 Exclusion criteria (must)**

- Declaration that all baseline subjects meeting any of the exclusion criteria will be excluded from the study

- 1) Other than NPC, the subject had any other malignancy within 2 years prior to enrollment. Subjects who have been cured by local treatment of other tumors, such as basal or cutaneous squamous cell carcinoma, superficial bladder cancer, cervix or breast in situ carcinoma, are not excluded.
- 2) Attreatment the investigational drug within 4 weeks prior to the first study administration.
- 3) Having active autoimmune diseases requiring systemic therapy over the past two years (e. g. use of modifying medication, corticosteroids, immunosuppressive therapy), alternative therapy (e. g., thyroxine, insulin, or physiological corticosteroid replacement therapy for adrenal or pituitary insufficiency) is not considered a systemic therapy.
- 4) History of immunodeficiency; test positive for HIV antibodies; ongoing use of systemic corticosteroids or other immunosuppressants.
- 5) Active TB should be excluded in subjects with suspected active TB (TB).
- 6) Known history of allogeneic organ transplantation and allogeneic HSCT.
- 7) For subjects with untreated active hepatitis B (HBsAg positive with HBV-DNA over 1 000 copies / ml (200 IU / ml) or above the lower limit of testing, whichever higher), anti-hepatitis B treatment was required during study treatment; subjects with active hepatitis C (HCV antibody positive and HCV-RNA levels above the lower limit of testing).
- 8) Major surgery or severe trauma within 30 days prior to the first dose, or a major surgical planner within 30 days after the first dose (at the discretion of the investigator); a minor local procedure (excluding transperipheral venous

puncture central venous catheterization) within 3 days prior to the first dose.

- 9) The presence of CNS metastases.
- 10) Current uncontrolled concurrent conditions, including but not limited to symptomatic congestive heart failure (grade 2 or above under the New York Heart Association functional classification), unstable angina, acute myocardial ischemia, poorly controlled arrhythmia, decompensated cirrhosis, nephrotic syndrome, uncontrolled metabolic disorders, severe active peptic ulcer disease or gastritis, or psychiatric / social conditions that may limit study requirements or affect the subject's ability to provide written informed consent.

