- 11) There was a past history of myocarditis, cardiomyopathy, and malignant arrhythmia. Unstable angina, congestive heart failure, or vascular disease (such as aortic aneurysm or peripheral venous thrombosis requiring surgical repair) within 2 months before the first dose, Or other cardiac lesions that may affect the safety evaluation of the study drug (e. g. poorly controlled arrhythmias, Myocardial infarction or ischemia); presence of esophageal-gastric varices within 6 months before the first dose, Severe ulcer, The wound has not healed, gastric-intestinal perforation, abdominal pain, Gastrointestinal obstruction, History of intra-abdominal abscess or acute gastrointestinal bleeding; any arterial thromboembolic event within 6 months prior to the first dose, NC I CTCAE 5.0 grade 3 and above, Transient cerebral ischemic attack, cerebrovascular accident, Hypertensive crisis or hypertensive encephalopathy; acute exacerbation of chronic obstructive pulmonary disease within 1 month before the first dose; current presence of hypertension with SBP> 160mmHg or DBP <100mmHg after oral antihypertensive medication.
- 12) History of severe bleeding tendency or coagulationopathy; blood symptoms of significant clinical significance within 1 month before the first dose, including but not limited to gastrointestinal bleeding, hemoptysis, screening imaging showing tumor wrapping around important blood vessels or significant necrosis and emptiness, and the investigator believes that participation in the study may

cause bleeding risk;

13) No response of prior anti-tumor therapy, defined as not returning to Grade 0 of NC 1 CTCAE 5.0 or 1, or the level specified in the inclusion / exclusion criteria, except for sequelae of alopecia, neurotoxicity associated with prior lead therapy. Subjects with irreversible toxicity not expected to worsen after study drug administration (e. g. hearing loss) may be included in the study after consultation with the medical monitor. Long-term toxicity from radiotherapy, subjects not recoverable as judged by the investigator may be included in the study after consultation with the medical monitor.

14) Live vaccination was administered within 30 days before the first dose, or was planned to be administered during the study period.

15) Known allergy to any component of any study drug; known history of severe hypersensitivity to other monoclonal antibodies.

16) Known history of mental illness, substance abuse, alcohol abuse, or drug use.

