17) Pregnant or lactating women.

18) Prior or current presence of any disease, treatment, laboratory abnormalities that may confuse the findings, affect the subject's full participation, or participation in the study may not be in the subject's best interest at the time.

19) Local or systemic disease due to nonmalignancy, or disease or symptoms secondary to tumor, and can lead to higher medical risk and / or uncertainty in survival evaluation, such as leukemic response (white cell count  $> 20 \times 10^9 / L$ ) or malmalignant manifestations (such as known weight loss of more than 10% in the 3 months prior to screening).

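### Exclusion 13 exempts neurotoxicity from earlier 'lead' (read as platinum) therapy from the recovery rule with no grade limit or medical-monitor step, and whoever enters this way is given platinum

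*Protocol*

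**What the plan says.** Protocol section 4.3, item 13, excludes subjects whose toxicity from prior anti-tumor therapy has not come back to CTCAE 5.0 grade 0 or 1, "or the level specified in the inclusion / exclusion criteria". It then makes an outright exception: "except for sequelae of alopecia, neurotoxicity associated with prior lead therapy".

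Two further sentences in the item deal with other residual toxicities, and both attach conditions. The first covers "Subjects with irreversible toxicity not expected to worsen after study drug administration", and continues: "e. g. hearing loss) may be included in the study after consultation with the medical monitor". The second concerns long-term radiotherapy toxicity: "subjects not recoverable as judged by the investigator may be included in the study after consultation with the medical monitor".

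The regimen appears in the scenario summary (research design) and in section 3.1. It is AK 104 plus platinum-based chemotherapy in 21-day cycles for the single arm of about 30 subjects; the summary gives 4-6 cycles of chemotherapy. The platinum agent is not named.

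**The concern.** Item 13 is the entry safeguard for damage left by earlier treatment. It is loosest for the toxicity that this regimen could plausibly aggravate. On the platinum reading, the exempted neurotoxicity was caused by the drug class that the study then gives. Even so, the item asks for more scrutiny of hearing loss and late radiotherapy effects than of neuropathy.

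Patient safety is what is at stake. Followed as written, the item lets a subject with unrecovered platinum neuropathy start platinum without anyone recording that the neuropathy is unlikely to worsen, and without the monitor being consulted.

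**Working it through.** No arithmetic applies, because the plan states no figure on this point. The check compares the routes in item 13 and then looks for a limit elsewhere.

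**Step 1: the routes within item 13.**

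| Residual toxicity | Grade limit | Must not be expected to worsen | Medical-monitor consultation |
|---|---|---|---|
| Alopecia | none | no | no |
| Neurotoxicity from prior 'lead' therapy | none | no | no |
| Irreversible toxicity, e.g. hearing loss | none | yes | yes |
| Unrecovered long-term radiotherapy toxicity | none | no (investigator judges it not recoverable) | yes |
| Everything else | grade 0-1, or a level given elsewhere in the criteria | not applicable | not applicable |

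Neurotoxicity sits with alopecia, which poses no comparable hazard on re-treatment, and not with the two conditional routes.

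**Step 2: is a level given elsewhere?** Item 13 allows for levels set in other criteria. Section 4.2 has 6 numbered inclusion items and section 4.3 has 19 exclusion items. None gives a neurotoxicity grade, so the exemption has no ceiling.

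**Step 3: the reading of 'lead'.** Section 1.3 describes treatment of advanced or recurrent disease as mainly platinum-containing chemotherapy, and the study regimen is platinum-based. Platinum is the reading that makes sense of the sentence, but it remains an inference. If it were wrong, the re-exposure argument would fall and only an uncapped exception would be left.

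**Step 4: who is re-exposed.** Platinum is planned for every subject. A subject who uses the exemption has, by its terms, had the earlier therapy that caused the neurotoxicity. For that subject, study platinum is a repeat exposure.

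**Step 5: other protections.**
- Inclusion 2 ("The Eastern Cooperative Oncology (ECOG) physical performance score was 0 or 1") restricts entry to subjects with good general function.
- Exclusion 10 ("Current uncontrolled concurrent conditions, including but not limited to symptomatic congestive heart failure") is open-ended but does not mention neuropathy.
- Exclusion 18 ("Prior or current presence of any disease, treatment, laboratory abnormalities that may confuse the findings") extends to cases where taking part may not serve the subject's best interest, which calls for an investigator judgement.
- The dose-adjustment rules in section 8 concern AK 104; none addresses platinum neurotoxicity.
- Section 4.4 provides for exit on unacceptable toxicity, which acts only after the harm.

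These narrow the gap. None sets a neurotoxicity grade or brings in the medical monitor.

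**The case against.** The strongest objection is that the argument leans on fine wording in a poorly translated item. 'Lead' has to be replaced before the point exists, the item's opening words do not fit the definition that follows, and the word sequelae may govern neurotoxicity as well as alopecia, which would suggest settled effects. This is a fair reason for caution. But a settled neuropathy can still worsen under more platinum, and that reading supplies neither a grade nor a review step.

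Second, the irreversible-toxicity sentence may already cover neuropathy, since hearing loss is only an example. A careful site could apply it so. The text does not require it: neurotoxicity has been exempted one sentence earlier and needs no further permission.

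Third, the exemption may be deliberate. Section 1.2 describes a population without a standard treatment, and residual neuropathy could otherwise keep out pretreated patients. That is a defensible aim, and the remedy below keeps such patients eligible through a review step.

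Four stronger readings are tempting and are not supported:
- *Every subject receives platinum a second time.* Inclusion 5 requires only prior PD-1 inhibitor failure, so repeat exposure is established only for those who use the exemption.
- *Nobody assesses these subjects.* Exclusion 18 already asks for a judgement on each subject; what is missing is a grade and the monitor's involvement.
- *Neuropathy of a particular severity will be enrolled.* Nothing in the Protocol links ECOG score to neuropathy grade or reports how common residual neuropathy is.
- *The trial's results are distorted.* Nothing in the document shows an effect on ORR, PFS or the AK 104 safety findings.

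**Conclusion.** The point holds as a minor patient-safety weakness in a stated eligibility rule. Item 13 lets residual neurotoxicity from earlier platinum pass with less scrutiny than hearing loss or late radiotherapy effects, although platinum is planned for everyone enrolled.

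Its size cannot be given. The Protocol does not say how many candidates carry such neurotoxicity, so the number admitted this way may be zero. With the platinum agent unnamed, the risk of worsening cannot be estimated either.

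The conclusion rests on two assumptions: that 'lead' means platinum, and that the exception is applied as printed, without borrowing the conditions of the sentence after it.

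**What to change.** Keep the unconditional exception in item 13 for alopecia only, and send neurotoxicity through the review route the item already has, with wording such as:

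> Residual neurotoxicity from prior platinum above grade 1 may be included only if not expected to worsen with AK 104 or the study platinum, after consultation with the medical monitor.

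Naming both AK 104 and the study platinum leaves no doubt about which treatment the judgement covers. Record the baseline CTCAE grade of each subject admitted this way, so that later worsening can be recognised. Replace 'lead' with the intended word in the same edit.

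The cost is one reworded sentence, one recorded baseline item and a few more consultations for the medical monitor. A few otherwise eligible subjects may not be entered.

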#### 4.4 Subject Exit Criteria (if any)

- ① Treatment failure as specified in the protocol occurs.
- ② Unacceptable treatment toxicity occurs.
- ③ Diseases that may significantly affect clinical status assessment or require interruption of treatment.
- ④ Patients may withdraw from this study at any time and for any reason.

Withdrawal procedure: Patients should be asked about the reason for their withdrawal and any adverse events occurring and, if possible, should be observed and evaluated by the investigator. Serious or unexpected adverse reactions should be followed-up. Once the patient withdraws or discontinues the trial, the investigator should try to obtain information about the patient. The investigator should do his best to complete the final evaluation and record their efforts. The results of these evaluations and observations, together with the description of the reasons for patient withdrawal, must be recorded in the original data. The primary reasons for withdrawal or discontinuation must be documented in the case report form (CRF) and the relevant follow-up study steps (discharge visit) completed whenever possible.

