## **3. research design**

### **3.1 Overall design (must)**

This study is a Phase II clinical study of carradilimumab (AK 104) plus chemotherapy for PD-1 inhibitor-resistant nasopharyngeal cancer to evaluate the safety and efficacy of carradilimumab plus chemotherapy as second-line and above treatment for PD-1 inhibitor-resistant nasopharyngeal cancer. This study is a single-arm, phase II clinical study with approximately 30 PD-1 inhibitor-resistant NPC subjects scheduled to be enrolled. PD-L1 CPS (<50% vs > 50%, subjects whose PD-L1 expression was not evaluated were classified as <50%) were used as the stratification factor. The study will have a safe lead-in period of approximately 6 PD-1 inhibitor-resistant subjects, and the investigator will conduct an preliminary safety assessment. If the safety and tolerance are good and initial efficacy signals are observed, the extended enrollment phase will enter. Efficacy analysis will be performed for approximately 15 subjects. If 6 of the 15 subjects are not tolerated,

subject enrollment may be stopped after the investigator discussion. After poor safety, the investigator decided to revise or stop the study. For 4-6 cycles, the use of calduilizumab until the investigator determines that there is no clinical benefit (based on the comprehensive judgment of RECISTv1.1 imaging assessment and clinical symptoms), toxicity intolerance, completion of 24 months of treatment, or satisfaction of other criteria for treatment termination in the regimen, whichever occurs first.

- Subject treatment protocol:
- Carradilizumab (200 mg, administered on day 1 of each cycle, Q3W until no longer had clinical benefit) + platinum was based chemotherapy, 1 treatment cycle every 3 weeks (21 days).

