**Table 1 Treatment adjustments for infusion response symptoms caused by AK**

104	
NCI-CTCAE grade	Regarding the treatment adjustment for AK 104
Level 1 mild Minor, temporary reaction; no infusion	Reduce the AK 104 infusion rate by 50% and closely monitor any deterioration. The total infusion time of AK 104 should not

interruption; no treatment.	exceed 120 minutes.

Level 2 moderate
 
Treatment or infusion interruption is required, but symptomatic treatment (such as antihistamines, NSAID, corticosteroids, intravenous infusion), rapid effect; preventive administration of <24 hours.
	
Interrupt the AK104 infusion.
 
The infusion was restarted at 50% of the previous infusion rate at times when the infusion response had subsided or the severity had dropped to at least level 1, and any deterioration was monitored closely.
 
If the subject has a second level 2 infusion reaction at a slower infusion rate, the infusion should be discontinued and the subject must be withdrawn from AK 104 treatment.

Grade 3 or 4 is serious or life-threatening
 
Grade 3: delay in symptom relief (e. g. symptomatic treatment and / or infusion interruption, lack of rapid response); relapse after symptom improvement; sequelae requiring hospitalization.
 
Grade 4: life-threatening; requiring urgent treatment.
	
The AK 104 infusion was stopped immediately, and the subject's infusion tube was disconnected.
 
Subjects must immediately withdraw from AK 104 treatment and must not receive any further AK 104 treatment.

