#### 8.4 Immune-related adverse events (irAE)

The irAE is defined as an AE associated with drug exposure, consistent with an immune-mediated mechanism of action, and without a clear alternative etiology.

Based on the mechanism of action of AK 104 targeting PD-1 and CTLA-4 leading to T cell activation and proliferation, it is possible that irAE could be observed during the conduct of this study. The underlying irAE may be similar to the adverse events seen with anti-PD-1 / L1 drugs, including immune-mediated colitis, dermatitis, pneumonia, hepatitis, encephalitis, nephritis, and endocrine disorders. Subjects should be monitored for the signs and symptoms of an irAE. In the absence of other alternative causes (e. g., infection or PD), immune-related causes associated with signs or symptoms of colitis, dermatitis, pneumonia, hepatitis, encephalitis, nephritis, and endocrine disorders should be considered.

Based on the severity of toxicity occurring in treatment according to NCI CTCAE 5.0 grade, AK 104 treatment adjustments will be performed to manage potential irAEs.

- The maximum interval allowing an AK 104 pause is 12 weeks. If they could not return to the reuse of AK 104 within 12 weeks, the subject permanently discontinued AK 104 and entered the follow-up phase. Except: AK 104 was suspended for more than 12 weeks or AK 104 for more than 12 weeks due to AEs that may be unrelated or unrelated to AK 104. In this case, a discussion with the medical monitor is needed to decide whether the AK 104 treatment can be continued.

Generally, it is recommended to manage irAEs according to the following principles. Subjects should be comprehensively evaluated, excluding any other alternative etiology (e. g. disease progression, concomitant medication, infection, etc.). Serological, immunological, and histological (biopsy) data should be used to support the diagnosis of irAE, as appropriate.

- If applicable, systemic corticosteroids (e. g., prednisone or intravenous equivalent) should be considered for persistent low-grade or severe (grade 3) events.

- If symptoms recur or worsen during the glucocorticoid reduction, the dose was increased until the symptoms stabilized or improved, and then gradually rereduced at a slower rate.
- For events that do not respond to systemic corticosteroids, more potent immunosuppressive agents (e. g. infliximab, maccohenyl esters, etc.) should be considered after discussion with the medical monitor.

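### Section 4.4 treats treatment failure, toxicity and disease needing treatment interruption as leaving the study, which conflicts with Section 8.4 and, read literally, ends systematic survival follow-up

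*Protocol*

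**What the plan says.** Section 4.4 of the protocol has four exit criteria. The first three are "Treatment failure as specified in the protocol occurs", "Unacceptable treatment toxicity occurs" and "Diseases that may significantly affect clinical status assessment or require interruption of treatment". The fourth is voluntary withdrawal, and it is the only one that names the study as the thing being left.

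A single withdrawal procedure follows: "Once the patient withdraws or discontinues the trial, the investigator should try to obtain information about the patient". The investigator is to make an effort at a final evaluation, with "the relevant follow-up study steps (discharge visit) completed whenever possible". The firmer duties are to follow serious or unexpected reactions and to record results and reasons. Survival follow-up is not mentioned.

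Other sections describe similar events as follows.
- Section 3.1 (and the scenario summary): AK 104 continues until loss of clinical benefit, "toxicity intolerance, completion of 24 months of treatment, or satisfaction of other criteria for treatment termination in the regimen, whichever occurs first".
- Table 1, second grade 2 infusion reaction: "the infusion should be discontinued and the subject must be withdrawn from AK 104 treatment".
- Section 8.4: AK 104 may be paused for up to 12 weeks. After a longer pause for adverse events unrelated to AK 104, continuation may be discussed with the medical monitor. Otherwise "the subject permanently discontinued AK 104 and entered the follow-up phase".

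PFS is a primary endpoint and OS a secondary one (Sections 2.2.1 and 2.2.2). The scenario summary gives three years of participation per subject.

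**The concern.** Stopping a drug and leaving a trial have different consequences for the data. A subject who stops treatment can still contribute scans and survival status; a subject who has left contributes only what was collected before. Section 4.4 merges the two, and Section 8.4 keeps them apart.

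The endpoint most exposed is OS. Most deaths in this population can be expected after treatment has failed. If follow-up becomes best effort at that moment, subjects are censored just when their risk of death rises. The Kaplan-Meier method assumes that censored subjects share the later risk of those still followed, which would not hold here. An analysis plan can set censoring rules, but it cannot recover survival status that was never collected.

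There is also an operational cost: two subjects with the same kind of intercurrent disease could be handled differently, one leaving the study under 4.4 and the other paused under 8.4.

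**Working it through.** **1. Which sections actually conflict**

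| Event | Section 4.4 | Elsewhere | Conflict? |
|---|---|---|---|
| Toxicity that ends AK 104 | Exit criterion, withdrawal procedure | 8.4: stops AK 104, moves to follow-up | Yes, outright |
| Disease requiring interruption | Exit criterion | 8.4: pause allowed, longer pause possible for unrelated events | Yes |
| Loss of benefit, intolerance | Exit criterion (as treatment failure or toxicity) | 3.1: ends AK 104 | 3.1 is silent on study status |
| Second grade 2 infusion reaction | Exit criterion if judged unacceptable toxicity | Table 1: withdrawn from AK 104 | Table 1 is silent on study status |

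The second row holds for intercurrent disease because Section 6.1 counts any adverse medical event after entry as an adverse event, whatever its cause, and the exception in 8.4 expressly covers unrelated events.

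**2. Is follow-up after treatment intended?** Apparently yes. Section 8.4 names a follow-up phase, OS is an endpoint, and three years of participation exceed the 24-month treatment cap in 3.1 by 12 months. On this evidence the wording of 4.4 runs against the protocol's own intent.

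**3. OS.** The size of the bias depends on when treatment fails, on survival after failure and on the share of subjects still contacted. The protocol gives none of these for this regimen. Only a direction can be stated: probably upward, or a median that is not reached.

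**4. PFS.** An exit at RECIST progression costs PFS nothing, since the event has been recorded. Only exits without progression matter.

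*Input.* Section 1.1.2 reports 6.6% withdrawal for treatment-related events among 228 subjects on AK 104 alone. 0.066 × 228 = 15.0, so 15/228, with a Clopper-Pearson 95% interval of 3.7% to 10.6%. Among 30 subjects: 30 × 0.066 = 2.0, interval 1.1 to 3.2.

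*Model (assumption).* Exponential PFS with on-treatment hazard L. A proportion p exits for toxicity, with hazard kL afterwards. Kaplan-Meier with censoring at exit estimates exp(−Lt). The true curve is:
- exits spread over time, with M = Lp/(1−p): S(t) = exp(−(L+M)t) + M[exp(−kLt) − exp(−(L+M)t)]/(L+M−kL);
- all exits at the start: S(t) = (1−p)exp(−Lt) + p·exp(−kLt).

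*Ratio of true median to Kaplan-Meier median* (it does not depend on L):

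| p | k | Spread | At start |
|---|---|---|---|
| 6.6% | 0.5 | 1.01 | 1.04 |
| 6.6% | 1 | 1.00 | 1.00 |
| 6.6% | 2 | 0.98 | 0.95 |
| 6.6% | 3 | 0.97 | 0.93 |
| 10.6% | 2 | 0.97 | 0.93 |
| 10.6% | 3 | 0.95 | 0.89 |

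*For comparison, sampling error.* The 95% confidence factor for an exponential median is exp(1.96/√d). That is 1.55 at d = 20 events and 1.45 at d = 28 (assumed event counts). It is far larger than any ratio in the table.

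**The case against.** The strongest reply is that this is a translation problem. The text is visibly machine-translated, only the fourth criterion names the study, and the first three may simply mean end of treatment. The word rendered as interruption may mean permanent stopping. The flow chart is not visible, so a follow-up schedule may exist. All of this stands, and it makes the harm conditional on a literal reading. It does not remove the defect: even if the first three criteria mean end of treatment, the heading and the shared procedure for patients who leave the trial would be wrong for them.

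A reader might also infer several stronger points that the documents do not support.
- *Sections 3.1, Table 1, 8.4 and 8.5 all contradict 4.4.* Only 8.4 says where the subject goes after AK 104 stops. Section 3.1 and Table 1 speak of treatment and leave study status open. The suspend-and-continue rule in 8.5 is limited to AK 104-related, non-immune events of grade 3 or above, so it does not show a conflict for intercurrent disease.
- *Treatment failure has no meaning in the protocol.* It may well point to the loss-of-benefit rule in 3.1. What is missing is the link.
- *The 24-week follow-up condition in the scenario summary is breached by toxicity exits.* That condition sets when the primary analysis is run; it is not a follow-up duty for each subject.
- *The primary PFS result is materially biased.* At the documented toxicity rate it is not, and the direction reverses if the hazard falls after exit (k = 0.5).

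Finally, the study is exploratory, with 30 subjects and no formal hypothesis, and OS is secondary. That lowers the priority without making the two sections agree.

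**Conclusion.** The concern holds as a conflict between Sections 4.4 and 8.4, together with an unlinked term and one procedure serving different situations. Its weight rests on OS: followed literally, 4.4 would turn survival follow-up after treatment failure or toxicity into best effort, with informative censoring that probably biases OS upward. The size cannot be computed from the documents, and the harm depends on sites reading 4.4 as written.

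The PFS effect does not carry the point. With 6.6% toxicity exits and a post-exit hazard 0.5 to 3 times that on treatment, the true median is 0.93 to 1.04 times the Kaplan-Meier median; the lowest value at the upper limit of 10.6% is 0.89. This assumes exponential times, a monotherapy withdrawal rate applied to the combination with chemotherapy, and that rate taken as stopping for toxicity. The documents give no rate for exits on clinical judgement or intercurrent disease without RECIST progression.

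It should be corrected, at modest priority.

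**What to change.** Reconcile Section 4.4 with Sections 3.1 and 8.4:
- Treat pausing treatment, stopping study treatment and leaving the study as three separate things, and apply the withdrawal procedure only to the last.
- Point treatment failure to its definition, for example the loss-of-benefit rule in 3.1, if that is what is meant.
- State that subjects who stop treatment stay on study for survival follow-up, and for the tumour assessments PFS needs if they have not progressed, unless they withdraw consent to follow-up.

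Which of the conflicting interruption or stopping rules applies is for the sponsor and investigator to settle; nothing here changes or proposes one.

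The cost is protocol wording, survival contacts that OS needs in any case, and scans for the few subjects who stop before progression (about 2 of 30 for toxicity at the documented rate).
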